5.2 Safety assessments

5.2.1 Laboratory safety assessments

Blood and urine samples for determination of clinical chemistry, haematology, coagulation, and urinalysis will be taken at the times indicated in the Study Plan (see [Table 1](#)).

Blood samples will be measured by SRL Medisearch Inc.

The detailed procedure of sampling, handling and shipping is described in the standard operating procedure made by AstraZeneca. In addition, the PI ensures that samples are labelled and shipped in accordance with the Laboratory Manual and the Biological Substance, Category B Regulations (materials containing or suspected to contain infectious substances

that do not meet Category A criteria), see Appendix C ‘International Airline Transportation Association (IATA) 6.2 Guidance Document’. Any samples identified as Infectious Category A materials are not shipped and no further samples will be taken from the subject unless agreed with AstraZeneca and appropriate labelling, shipment and containment provisions are approved.

Urinalysis will be performed at each study site by dipstick provided by SRL Medisearch Inc.

The following laboratory variables will be measured:

Table 2 Laboratory Safety Variables

Haematology/Haemostasis	Clinical Chemistry
B-Haemoglobin (Hb)	S-Creatinine
B-Leukocyte count	S-Bilirubin, total
B-Leukocyte differential count (absolute count)	S-Alkaline phosphatase (AP)
B-Platelet count	S-AST
B-Haematocrit	S-ALT
P-PT	S-Albumin
P-PTT	S-Potassium
Urinalysis	S-Calcium, total
U-Hb	S-Sodium
U-Protein/Albumin	S-Creatine kinase (CK)
U-Glucose	S-TSH
U-Pregnancy	B-HbA1c
	P-Glucose
	S-LDL-C
	S-Apo B

The Investigator should make an assessment of the available results with regard to clinically relevant abnormalities. The laboratory results should be signed and dated and retained at site as source data for laboratory variables. For information on how AEs based on laboratory tests should be recorded and reported, see Section 6.3.

5.2.2 Physical examination

5.2.2.1 Brief Physical Findings

A brief physical findings will be performed and include an assessment of the following: general appearance, respiratory, cardiovascular, abdomen, skin, head and neck (including ears,

eyes, nose and throat), lymph nodes, thyroid, musculo-skeletal (including spine and extremities) and neurological systems.

5.2.2.2 Clinical Assessments

Subjects will be questioned by investigators at every visit regarding the occurrence and nature of any symptoms and signs. Body weight will be measured at each time, however, height will be measured only at Visit 1 to determine the BMI.

5.2.3 ECG

For timing of assessments refer to the Study Plan ([Table 1](#)).

A 12-lead ECG will be performed after patient has been supine at rest for at least 5 minutes.

All ECGs will be evaluated for heart rate, QT interval, ECG interval measured from the onset of the QRS complex to the onset of the P wave (PR), ECG interval measured from the onset of the QRS complex to the J point (QRS), and the time between corresponding points on 2 consecutive R waves on ECG (RR) intervals from the 12-lead ECG, and the Investigators will judge the overall interpretation as normal or abnormal. If abnormal, it will be decided as to whether or not the abnormality is clinically significant and the reason for the abnormality will be recorded. ECG will be measured using the same recording device during this study as much as possible.

All ECG readings will be stored as source documents as a paper printout if the data will not be able to be kept electronically.

5.2.4 Vital signs

BP and pulse will be measured by standard BP recording device using at study site(s) with an appropriate cuff size. BP and pulse will be measured using the same recording device during this study as much as possible.

For timings of assessments refer to the Study Plan ([Table 1](#)).

5.3 Other assessments (Not Applicable)

5.4 Pharmacokinetics (Not Applicable)

5.5 Pharmacodynamics (Not Applicable)

5.6 Pharmacogenetics (Not Applicable)

5.7 Biomarker analysis (Not Applicable)

6. SAFETY REPORTING AND MEDICAL MANAGEMENT

The PI is responsible for ensuring that all staff involved in the study are familiar with the content of this section.

6.1 Definition of adverse events

An AE is the development of an undesirable medical condition or the deterioration of a pre-existing medical condition following or during exposure to a pharmaceutical product, whether or not considered causally related to the product. An undesirable medical condition can be symptoms (e.g., nausea, chest pain), signs (e.g., tachycardia, enlarged liver) or the abnormal results of an investigation (e.g., laboratory findings, ECG). In clinical studies, an AE can include an undesirable medical condition occurring at any time, including screening periods, even if no study treatment has been administered.

The term AE is used to include both serious and non-serious AEs.

6.2 Definitions of serious adverse event

A SAE is an AE occurring during any study phase (i.e., screening and treatment), that fulfils one or more of the following criteria:

- Results in death
- Is immediately life-threatening
- Requires in-patient hospitalisation or prolongation of existing hospitalisation
- Results in persistent or significant disability/incapacity or substantial disruption of the ability to conduct normal life functions
- Is a congenital abnormality or birth defect
- Is an important medical event that may jeopardise the subject or may require medical intervention to prevent one of the outcomes listed above.

For further guidance on the definition of a SAE, see Appendix B to the Clinical Study Protocol.

6.3 Recording of adverse events

6.3.1 Time period for collection of adverse events

AEs will be collected from randomisation (Visit 4) until Visit 18 (or Visit 19).

SAEs will be recorded from the time of informed consent (Visit 1) until Visit 18 (or Visit 19).

6.3.2 Follow-up of unresolved adverse events

Any AEs that are unresolved at the subject's last visit in the study are followed up by the investigator for as long as medically indicated, but without further recording in the eCRF. AstraZeneca retains the right to request additional information for any subject with ongoing AE(s)/SAE(s) at the end of the study, if judged necessary.

6.3.3 Variables

The following variables will be collected for each AE:

- AE (verbatim)
- The date when the AE started and stopped
- Maximum Intensity
- Whether the AE is serious or not
- Investigators causality rating against the investigational product (yes or no)
- Action taken with regard to investigational product
- AE caused subject's withdrawal from study (yes or no)
- Outcome

In addition, the following variables will be collected for SAEs:

- Date AE met criteria for serious AE
- Date Investigators became aware of serious AE
- AE is serious due to
- Date of hospitalisation
- Date of discharge
- Probable cause of death
- Date of death
- Autopsy performed
- Causality assessment in relation to Study procedure(s)
- Description of AE

Intensity rating scale:

1. mild (awareness of sign or symptom, but easily tolerated)
2. moderate (discomfort sufficient to cause interference with normal activities)
3. severe (incapacitating, with inability to perform normal activities)

It is important to distinguish between serious and severe AEs. Severity is a measure of intensity whereas seriousness is defined by the criteria in Section 6.2. An AE of severe intensity need not necessarily be considered serious. For example, nausea that persists for several hours may be considered severe nausea, but not a SAE unless it meets the criteria shown in Section 6.2. On the other hand, a stroke that results in only a limited degree of disability may be considered a mild stroke but would be a SAE when it satisfies the criteria shown in Section 6.2.

6.3.4 Causality collection

The PI will assess causal relationship between investigational product and each AE, and answer “yes” or “no” to the question “Do you consider that there is a reasonable possibility that the event may have been caused by the investigational product?”

For SAEs causal relationship will also be assessed for other medication and study procedures. Note that for SAEs that could be associated with any study procedure the causal relationship is implied as “yes”.

A guide to the interpretation of the causality question is found in Appendix B to the Clinical Study Protocol.

6.3.5 Adverse events based on signs and symptoms

All AEs spontaneously reported by the subject or reported in response to the open question from the study personnel: “Have you had any health problems since you were last asked?”, or revealed by observation will be collected and recorded in the eCRF. When collecting AEs, the recording of diagnoses are preferred (when possible) to recording a list of signs and symptoms. However, if a diagnosis is known and there are other signs or symptoms that are not generally part of the diagnosis, the diagnosis and each sign or symptom will be recorded separately.

6.3.6 Adverse events based on examinations and tests

The results from protocol mandated laboratory tests, vital signs, ECGs and other safety assessments will be summarised in the clinical study report. Deterioration as compared to baseline in protocol-mandated laboratory values, vital signs, ECGs and other safety assessments should therefore only be reported as AEs if they fulfil any of the SAE criteria or are the reason for discontinuation of treatment with the investigational product.

If deterioration in a laboratory value or vital sign is associated with clinical signs and symptoms, the sign or symptom will be reported as an AE and the associated laboratory result or vital sign will be considered as additional information. Wherever possible the reporting investigator uses the clinical, rather than the laboratory term (e.g., anaemia versus low Hb value). In the absence of clinical signs or symptoms, clinically relevant deteriorations in non-mandated parameters should be reported as AE(s).

Any new or aggravated clinically relevant abnormal medical finding at a physical examination as compared with the baseline assessment will be reported as an AE.

6.4 Reporting of serious adverse events

All SAEs have to be reported, whether or not considered causally related to the investigational product, or to the study procedure(s). All SAEs will be recorded in the eCRF.

If any SAE occurs in the course of the study, then investigators or other site personnel inform appropriate AstraZeneca representatives promptly, or **no later than 24 hours** of when he or she becomes aware of it.

The designated AstraZeneca representative works with the investigator to ensure that all the necessary information is provided to the AstraZeneca patient safety data entry site **within one calendar day** of initial receipt for fatal and life threatening events **and within five calendar days** of initial receipt for all other SAEs.

For fatal or life-threatening AEs where important or relevant information is missing, active follow-up is undertaken immediately. Investigators or other site personnel inform AstraZeneca representatives of any follow-up information on a previously reported SAE promptly, or **no later than 24 hours** of when he or she becomes aware of it.

Once the investigator or other site personnel indicate an AE is serious in the WBDC system, an automated email alert is sent to the designated AstraZeneca representative.

If the WBDC system is not available, then the investigator or other study site personnel reports a SAE to the appropriate AstraZeneca representative by telephone.

The AstraZeneca representative will advise the investigator/study site personnel how to proceed.

6.5 Overdose

There are no human data on overdosing and no known antidote.

It will be considered the taking investigational product that is ≥ 5 capsules per day to be the overdose.

- An overdose with associated AEs is recorded as the AE diagnosis/symptoms on the relevant AE modules in the eCRF and on the Overdose eCRF module.
- An overdose without associated symptoms is only reported on the Overdose eCRF module.

If an overdose on an AstraZeneca study drug occurs in the course of the study, then the Investigator or other site personnel inform appropriate AstraZeneca representatives immediately, or **no later than 24 hours** of when he or she becomes aware of it.

The designated AstraZeneca representative works with the Investigator to ensure that all relevant information is provided to the AstraZeneca Patient Safety data entry site.

For overdoses associated with a SAE, the standard reporting timelines apply, see Section 6.4. For other overdoses, reporting must be provided to the AstraZeneca Patient Safety data entry site within 30 days.

6.6 Pregnancy

All pregnancies and outcomes of pregnancy should be reported to AstraZeneca.

6.6.1 Maternal exposure

If a subject becomes pregnant during the course of the study, investigational product should be discontinued immediately.

Pregnancy itself is not regarded as an AE unless there is a suspicion that the investigational product under study may have interfered with the effectiveness of a contraceptive medication.

Congenital abnormalities/birth defects and spontaneous miscarriages should be reported and handled as SAEs. Elective abortions without complications should not be handled as AEs. The outcome of all pregnancies (spontaneous miscarriage, elective termination, ectopic pregnancy, normal birth or congenital abnormality) should be followed up and documented even if the subject was discontinued from the study.

If any pregnancy occurs in the course of the study, then the Investigator or other site personnel informs the appropriate AstraZeneca representatives promptly, or **no later than 24 hours** of when he or she becomes aware of it.

The designated AstraZeneca representative works with the Investigator to ensure that all relevant information is provided to the AstraZeneca Patient Safety data entry site within 1 or 5 calendar days for SAEs (see Section 6.4) and within 30 days for all other pregnancies.

The same timelines apply when outcome information is available.

The PREGREP module in the eCRF is used to report the pregnancy and the PREGOUT is used to report the outcome of the pregnancy.

6.6.2 Paternal exposure

There are no restrictions against fathering a child when treated with AZD0585.

If paternal exposure pregnancy occurs in the course of the study, then investigators or other centre personnel should inform appropriate AstraZeneca representatives within 24 hours as described in the maternal exposure Section 6.6.1.

6.7 Management of investigational product related toxicities (Not Applicable)

6.8 Study governance and oversight

6.8.1 Steering Committee

A Steering Committee will be set up in this clinical study. The Steering Committee charter will be prepared to detail responsibilities. The Steering Committee constitutions are presented in Supplement A.

7. INVESTIGATIONAL PRODUCT AND OTHER TREATMENTS

7.1 Identity of investigational product(s)

Table 3 Identity of investigational product(s)

Investigational product	Dosage form and strength	Manufacturer
AZD0585 capsule	1 g soft gelatine capsules [REDACTED] [REDACTED]	Catalent Germany Eberbach GmbH (encapsulation) Catalent Germany Schondorf GmbH (capsule coating / bulk packing)
AZD0585 capsule placebo	1 g soft gelatine capsules (corn oil)	Catalent Germany Eberbach GmbH (encapsulation) Catalent Germany Schondorf GmbH (capsule coating / bulk packing)

7.2 Dose and treatment regimens

Patients start treatment of AZD0585 administration at Visit 4 (Randomisation). Eligible patients will be randomly assigned to 1 of 3 treatment groups: AZD0585 2 g with placebo (corn oil) 2 g once daily, or AZD0585 4 g once daily, or placebo (corn oil) 4 g once daily. The capsules of AZD0585 and placebo are identical in appearance of 1 g soft gelatine capsules, and all patients will need to take 4 capsules once daily just after breakfast.

7.3 Labelling

Labels will be prepared in accordance with Good Clinical Practice (GCP) Ordinance. Details are specified in the document “explaining the reconstitution procedures and other handling procedures for the investigational products”.

7.4 Storage

All study drugs should be kept in a secure place under appropriate storage conditions.

A description of the appropriate storage conditions is specified in the document “explaining the reconstitution procedures and other handling procedures for the investigational products”.

7.5 Compliance

The administration of all study drugs (including investigational products) should be recorded in the appropriate sections of the eCRF.

The investigator(s) will check drug accountability. If the patient's compliance rate is low due to missing doses, etc, the investigator(s) will instruct the patient to comply with the treatment.

7.6 Accountability

The study drug provided for this study will be used only as directed in the study protocol.

Study drug will not be distributed to the study site until the contract is concluded between the study site and AstraZeneca. The Investigational Product Storage Manager is responsible for managing the study drug from receipt by the study site until the return of all unused study drug to AstraZeneca. AstraZeneca will provide the study documents 'Procedures for drug accountability' and 'explaining the reconstitution procedures and other handling procedures for the investigational products' which describes the specific requirements. The Investigator(s) is responsible for ensuring that the subject has returned all unused study drug.

7.7 Concomitant and other treatments

Concomitant use of following medications or therapies is not allowed during study period.

- Fibrates, bile acid sequestrants, or niacin or its analogues (greater than 200 mg/day) or any drug for the purpose of lowering plasma cholesterol (except for statin) from the screening to Visit 8.
- Any EPA or DHA products, fish oil, or medications (e.g., Lotriga[®], Epadel[®]) or investigational drugs (e.g., AMR101) containing EPA or DHA during study period.
- Any supplement for the purpose of lowering plasma cholesterol (e.g., red rice yeast supplements) from the screening to Visit 8.
- Weight loss drugs (including OTC preparations) or programs during study period.
- Ketoconazole, erythromycin, clarithromycin, cyclosporine, itraconazole, or protease inhibitors during study period only for statin users.
- Any anticoagulants (e.g., warfarin, coumarin, heparin, Prazaxa[®] or enoxaparin) during study period.
- Oral or injected corticosteroids (other than intranasal or inhaled steroids used for allergies/asthma) during study period.
- Grapefruit juice >750 mL/day during study period only for statin users.
- Insulin during study period.

Concomitant use of tamoxifen, estrogens, progestins, and testosterone are allowed during study period without change of the dose regimen, if the treatment of those drugs is stable during screening.

Fixed dose statin can be used until Visit 8. No limit is set to use statin after Visit 8.

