3.2 Exclusion criteria

Subjects must not be randomised in the study if any of the following exclusion criteria are fulfilled:

1. Allergy or intolerance to omega-3 fatty acids and omega-3-acid ethyl esters.
2. Use of fibrates, bile acid sequestrants, or niacin or its analogues (greater than 200 mg/day) or any drug for the purpose of lowering plasma cholesterol (except for statin) during screening.
3. Use of any EPA or DHA products, fish oil, or medications (e.g., Lotriga[®], Epadel[®]) or investigational drugs (e.g., AMR101) containing EPA or DHA within 8 weeks prior to randomisation.
4. Use of any supplement for the purpose of lowering plasma cholesterol during screening (e.g., red rice yeast supplements).
5. Use of weight loss drugs (including over-the-counter [OTC] preparations), supplements or programs during screening.
6. Use of anticoagulants (e.g. warfarin, coumarin, heparin, enoxaparin or Prazaxa[®]) during screening.
7. Use of oral or injected corticosteroids (other than intranasal or inhaled steroids used for allergies/asthma) during screening.

8. Use of tamoxifen, estrogens, progestins, or testosterone, that has not been stable for >4 weeks at Visit 1, or is unstable during screening.
9. Known lipoprotein lipase impairment or deficiency, or Apo C-II deficiency or familial dysbetalipoproteinemia.
10. Current or history of pancreatitis.
11. Type I diabetes mellitus, use of insulin, or haemoglobin A1c (HbA1c) >10% at Visit 1.
12. Poorly controlled hypertension (resting blood pressure [BP] \geq 160 mmHg systolic and/or \geq 100 mmHg diastolic) at two consecutive visits prior to randomisation at Visit 4.
13. Uncontrolled hypothyroidism, thyroid stimulating hormone (TSH) >1.5 x upper limit of normal (ULN) or Cushing's syndrome at Visit 1.
14. Within six months prior to Visit 1 or current significant nephritic syndrome, pulmonary, hepatic, biliary, gastrointestinal or immunologic disease.
15. Current or history of cancer (except non-melanoma skin cancer, or carcinoma in situ of cervix) within the previous five years.
16. Female patients who is considered of childbearing potential if she is not surgically sterile or if her last menstrual period was <12 months prior to Visit 1 meet any following criteria:
 - Have a positive pregnancy test
 - Be breast feeding
 - Be planning to be pregnant during the study period
 - Cannot use acceptable methods of contraception

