Acceptable methods of contraception for this study include use of double barrier contraception, intrauterine device or abstinence, all oral, hormonal or selective estrogen receptor modulator contraceptives as long as dose and type is stable for 3 months prior to Visit 1.
17. Creatine kinase >5.0 times ULN; AST or ALT >2.5 times ULN at Visit 2.
18. Current or within 12 months prior to Visit 1 of drug or alcohol abuse.
19. Exposure to any investigational agent within 4 weeks prior to Visit 1.

20. Any other condition the investigators believe would interfere with the subject's ability to provide informed consent, comply with study instructions, or which might confound the interpretation of the study results or put the subject at undue risk.
21. Patients who are at known risk for bleeding including congenital disorder of coagulation system, recent severe external injury and/or any known conditions that will require surgery during the study period.
22. Involvement in the planning and/or conduct of the study (applied to both AstraZeneca staff and/or staff at the study site)
23. Previous participation in a clinical study with AZD0585.

Procedures for withdrawal of incorrectly enrolled subjects see Section 3.4.

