4. STUDY PLAN AND TIMING OF PROCEDURES

Table 1 Study Plan

	Screening period				Treatment period													Withdrawal visit ^a				
	-8	-4	-2		0	4	8	10	12	16	20	24	28	32	36	40	44		48	52		
Week	1	2	3	3 ^a	4 ^c	5	6	7	8	9	10	11	12	13	14	15	16	17	18	19		
Visit window (days)	± 3	± 3	± 2		0	± 2	± 2	± 2	± 2	± 7	± 7	± 7	± 7	± 7	± 7	± 7	± 7	± 7	± 7	± 7		
Informed Consent	X																					
Eligibility Review	←				→																	
Randomisation					X																	
Demography	X																					
Medical History/Surgical History, Prior Medications	←				→																	
Brief Physical Findings ^d	X								X													X
Clinical Assessments ^e	X				X	X	X	X	X	X	X	X	X	X	X	X	X	X	X	X	X	X
Vital Sign	X				X	X	X		X	X	X	X	X	X	X	X	X	X	X	X	X	X
Fasting Lipid Panel (TG, TC, LDL-C, HDL-C, non-HDL-C, VLDL-C)	X	X	X	X	X	X	X	X	X	X	X	X	X	X	X	X	X	X	X	X	X	X
Fasting special lipid markers (RLP-C, Apo B and Apo B48)	X				X				X			X										X
Fatty acids profile (EPA, DHA, AA, and EPA/AA ratio)	X				X				X			X										X
Small dense LDL					X				X			X										X

Table 1 Study Plan

	Screening period				Treatment period														With- drawal visit ^a	
	-8	-4	-2		0	4	8	10	12	16	20	24	28	32	36	40	44	48		52
Week	1	2	3	3 ^a	4 ^c	5	6	7	8	9	10	11	12	13	14	15	16	17	18	19
Visit window (days)	± 3	± 3	± 2		0	± 2	± 2	± 2	± 2	± 7	± 7	± 7	± 7	± 7	± 7	± 7	± 7	± 7	± 7	
Apo except Apo B (A-I, A-II, C-II, C-III and E)					X				X			X			X				X	
hs-CRP					X				X			X			X				X	
Fasting special lipid markers (Lp(a), PCSK9)					X				X			X			X				X	
Clinical Chemistry	X	X			X	X			X	X		X			X				X	
Haematology	X	X			X	X			X	X		X			X				X	
Thromboplastin time (PT), Partial thromboplastin time (PTT)		X			X				X			X			X				X	
Urinalysis	X	X			X	X			X	X		X			X				X	
HbA1c	X				X				X			X			X				X	
Assessment of renal function (Estimated glomerular filtration rate [eGFR], Albumin Creatinine Ratio [ACR])	X																			
TSH	X																			
Urine Pregnancy Test	X				X														X	

Table 1 Study Plan

Week	Screening period				Treatment period														Withdrawal visit ^a			
	-8	-4	-2		0	4	8	10	12	16	20	24	28	32	36	40	44	48		52		
Visit	1	2	3	3a ^b	4 ^c	5	6	7	8	9	10	11	12	13	14	15	16	17	18	19		
Visit window (days)	± 3	± 3	± 2		0	± 2	± 2	± 2	± 2	± 7	± 7	± 7	± 7	± 7	± 7	± 7	± 7	± 7	± 7	± 7		
ECG	X				X				X			X			X					X		
Diet Counselling on Therapeutic Lifestyle Changes (TLC) diet	X	X	X		X	X	X	X	X	X	X	X	X	X	X	X	X	X	X			

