8.5.2.2 Safety variables

Safety for AZD0585 2 g and 4 g will be mainly evaluated via AEs, brief physical findings/clinical assessments, laboratory measurements, vital signs and ECGs.

The analysis of safety was based on the safety analysis set. Safety data obtained during the treatment period were evaluated descriptively by treatment group. No formal statistical hypothesis testing will be performed. Details will be specified in Statistical Analysis Plan.

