4.2.3.4	Vital signs	
4.2.3.5	Physical examination	
4.2.3.6	Electrocardiograms	
5.	INTERIM ANALYSES	24
6.	CHANGES OF ANALYSIS FROM PROTOCOL	24
7.	REFERENCES (NOT APPLICABLE)	
8.	APPENDIX (NOT APPLICABLE)	24
LIST (OF TABLES	
Table 1	List of important protocol deviations	12
Table 2	Transformation of quantities from log-transformed analysis	18
Table 3	Subgroup analyses of primary efficacy variable	19
Table 4	Liver enzyme abnormalities	23
Table 5	Categorical evaluation of QTcF	24
LIST (OF FIGURES	
Figure 1	Study flow chart	11

LIST OF ABBREVIATIONS

Abbreviation or special term	Explanation
AA	Arachidonic acid
AE	Adverse Event
ALP	Alkaline phosphatise
ALT	Alanine aminotransferase
ANCOVA	Analysis of covariance
Apo	Apo-lipoprotein
AST	Aspirate transferase
AT	Aminotransferase; short for ALT or AST
BMI	Body Mass Index
CI	Confidence Interval
DAE	AE leading to Discontinuation
DHA	Docosahexaenoic Acid
ECG	Electrodiagram
EPA	Eicosapentaenoic Acid
FAS	Full Analysis Set
HDL-C	High-density lipoprotein cholesterol
hs-CRP	High-sensitivity C-reactive protein
LDL-C	Low-density lipoprotein cholesterol
Lp(a)	Lipoprotein(a)
LS	Least squares
MAR	Missing At Random
MedDRA	Medical Dictionary for Regulatory Activities
MI	Multipile imputation
MMRM	Mixed model with repeated measures
OC	Observed Case
PCSK9	Proprotein convertase subtilisin/kexin type 9
PD	Protocol Deviation
PT	Preferred Term
QTcF	QT interval corrected by Fridericia Formula (= $QT / \sqrt[3]{RR}$)

Abbreviation or special term	Explanation
RLP-C	Remnant lipoprotein cholesterol
SAE	Serious Adverse Event
SMQ	Standard MedDRA Query
SOC	System Organ Class
TBIL	Total bilirubin
TC	Total cholesterol
TG	Triglyceride
ULN	Upper limits of normal
VLDL-C	Very-low-density lipoprotein cholesterol

AMENDMENT HISTORY

Date	Brief description of change
19Sep2016	Concomitant medications: summary of all prior/concomitant medications are changed to summary of all prior/concomitant medications excluding lipid lowering medications .
	Adverse events: the following two summaries are now taken out based on consideration of relevance for study report.
	- Most common AEs (i.e., reported by ≥ 2 % of subjects in any treatment group based on Preferred Terms)
	- AEs by treatment period (by Day 1-84, Day 85-168, Day 169-252, Day 253-336, Day 337- end of study)

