4.2.3.2 Adverse events

Treatment-emergent adverse events (TEAEs, i.e. adverse events with onset on or after first dose of study drug) will be summarized for safety evaluation. Adverse events occurring before start of study drug will only be listed.

Adverse events (AEs) will be classified by Primary System Organ Class (SOC) and Preferred Term (PT) according to the Medical Dictionary for Regulatory Activities (MedDRA). Summaries of AEs will use the version of MedDRA that is current at the time of database lock

All adverse events

All AEs with onset during the first 12-week (+2 days) treatment period, 24-week (+7 days) treatment period and with onset during the whole study treatment period will be summarized. The following items will be summarized by system organ class, preferred term and treatment group.

- Any AEs
- Deaths
- Serious AEs (SAEs)
- AEs leading to study drug discontinuation (DAEs)
- AEs by maximum intensity
- AEs related to study drug

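### The protocol guards against bleeding, but no table in SAP 4.2.3.2 counts patients with any bleeding event; one grouped descriptive table would supply that count cheaply

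*Protocol*

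**What the plan says.** **Guarding against bleeding.** Protocol 3.2 excludes anticoagulant users (no. 6) and "Patients who are at known risk for bleeding including congenital disorder of coagulation system" (no. 21, which also covers recent severe injury and expected surgery). Protocol 7.7 prohibits "Any anticoagulants (e.g., warfarin, coumarin, heparin" and others for the whole study. In Protocol Table 1, PT and PTT are scheduled at Weeks -4, 0, 12, 24, 36 and 52, and Table 2 lists them among the safety laboratory variables.

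**Safety analysis.** Long-term safety is one of two primary objectives, and adverse events are its first-listed outcome. Protocol 8.5.2.2 states "No formal statistical hypothesis testing will be performed" and leaves the detail to the SAP. SAP 4.2.3.2 covers any AE, deaths, SAEs, AEs leading to discontinuation, AEs by maximum intensity and drug-related AEs: "The following items will be summarized by system organ class, preferred term and treatment group". The SAP abbreviation list defines SMQ ("Standard MedDRA Query"), but no analysis section uses one.

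**Other safety topics.** The SAP adds a topic-specific table for liver enzymes (4.2.3.3, Table 4) and one for QTcF (4.2.3.6, Table 5). It has none for bleeding events.

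**The concern.** In the AE tables each event is counted under one primary SOC and one preferred term. SOCs follow body systems for the most part, so a nosebleed, a gastrointestinal bleed, a bruise and blood in the urine fall in different places. The number of patients with at least one bleed is then not in any planned table. It cannot be recovered by adding rows, because one patient may appear in several.

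The other planned outputs do not supply it. SOC rows add terms only within one SOC and mix bleeding with unrelated events. The SAE and discontinuation tables use the same two-level layout and show only part of the bleeding. PT/PTT summaries describe laboratory change. Under Protocol 6.3.6 a laboratory deterioration becomes an AE only if it meets an SAE criterion or is the reason for stopping treatment.

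What is at stake is how well the primary safety objective is served on a topic to which the protocol gives two exclusions, a prohibition and a laboratory row.

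**Working it through.** **The plan's own figures.** The documents give no bleeding rate and no precision statement for any AE. Their only power figure, at least 92% for TG, reproduces: SD 24, difference 12.5, 75 vs 150, two-sided 0.025, noncentral t with 223 df gives 92.2%. It is not affected by this point.

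**Inputs from the documents.** 75 placebo, 150 on 2 g, 150 on 4 g (Protocol 8.2); 300 when the doses are pooled.

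**Assumed inputs.** 52-week risk of any bleeding AE: 2% on placebo, 4% to 10% on AZD0585. Events are spread evenly over k = 5 to 10 preferred terms.

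**Yardstick.** How often the 95% CI for the risk difference lies above zero. The plan attaches no test or CI to AE rows, so this only measures visibility. Newcombe lower limit: (p1 - p0) - √[(p1 - l1)² + (u0 - p0)²], where l1 is the lower Wilson limit for AZD0585 and u0 the upper Wilson limit for placebo.

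**Step 1, with no assumed rate.** Take 0 of 75 on placebo: u0 = 3.84/(75 + 3.84) = 0.0487.
- 16 of 300: p1 = 0.0533, l1 = 0.0331, lower limit = 0.0533 - √(0.0202² + 0.0487²) = +0.0006.
- 15 of 300: p1 = 0.0500, l1 = 0.0305, lower limit = -0.0025.

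So even against an empty placebo cell, a row needs 16 of 300 pooled (5.3%). For one dose the corresponding threshold is 9 of 150 (6%).

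**Step 2, expected counts at 2% vs 8%.** Grouped row: 75 × 0.02 = 1.5 placebo, 150 × 0.08 = 12 per dose, 300 × 0.08 = 24 pooled. Split over 8 terms, each row expects 0.19 placebo, 1.5 per dose and 3 pooled, far below the Step 1 thresholds.

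**Step 3, chance that the CI lies above zero.** The grouped and half-SOC figures sum exact binomial probabilities; the any-row figures are simulated.

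| Placebo vs AZD0585 | Grouped, 300 vs 75 | Grouped, one dose, 150 vs 75 | SOC row holding half the bleeding, 300 vs 75 | Any single term row, k = 5 to 10, 300 vs 75 |
|---|---|---|---|---|
| 2% vs 4% | 3% | 4% | <0.1% | about 0% |
| 2% vs 6% | 19% | 16% | 1% | about 0% |
| 2% vs 8% | 42% | 37% | 7% | <0.1% |
| 2% vs 10% | 68% | 60% | 21% | up to 0.2% |

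At a higher background, 4% vs 12%, the pooled grouped figure is 55%. The SOC column is optimistic, because a real SOC row also holds non-bleeding events. All figures use randomised numbers; the 10-15% dropout in SAP 1.3 would lower them somewhat by shortening exposure.

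**The case against.** **Safety is descriptive, so a CI is the wrong test of visibility.** This largely stands. A medical reviewer reads patterns. At 2% vs 8% spread over 5 or 8 terms, at least three rows with two or more AZD0585 patients and none on placebo appear in about 85-98% of simulated trials. That is a visible cue, so a reader who inferred that a bleeding excess would go unseen would be going too far.

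The cue is not clean, however, because the pooled allocation is 4:1. With no excess at all (2% in every arm, 8 terms, 0.25% per term), the chance of two or more in 300 is 0.173 and of none in 75 is 0.829. That gives 8 × 0.173 × 0.829 = 1.1 such rows expected. At 4% in every arm it is 8 × 0.443 × 0.687 = 2.4. Nor does the pattern give a patient count or a size.

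**Grouping helps little for modest effects.** This stands. For a two- to threefold excess from 2%, the grouped CI excludes zero in only 3-19% of trials.

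**Bleeding is not a stated risk.** This stands as a limit. A reader might infer from the exclusions that bleeding is a recognised risk of AZD0585, but the documents never say so. Protocol 1.1 and 1.3 report the drug as safe and well tolerated and do not mention bleeding. The anticoagulant bar sits in a list with insulin, corticosteroids and grapefruit juice.

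**The grouping can be run later.** It can, since AEs are MedDRA-coded. But the sponsor is unblinded at the interim analysis (SAP 5), and a term list chosen after that is open to selection.

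**Conclusion.** The gap is real but limited. The plan has no count of patients with any bleeding event across SOCs, and its tables cannot be added up to give one, so an excess spread over several terms could easily be missed or could not be quantified. It does not follow that the AE analysis cannot address safety: SOC rows, the SAE and discontinuation tables and the pattern across terms all carry some information.

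On the assumed rates, grouping raises the chance that a CI excludes zero from about 0.2% or less (any single term row), or at most about 7-21% (a SOC row with half the bleeding), to about 42-68% for 2% vs 8-10%. For one dose these grouped figures are about 37% and 60%. For smaller excesses even the grouped row is weak, so the table would describe a signal and would not support a powered comparison. The rates, the even spread and the number of terms are all assumptions. The point is an optional, cheap improvement; no stated analysis is in error.

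**What to change.** Before the interim unblinding, add one descriptive table to SAP 4.2.3.2:

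- **Content:** patients with at least one treatment-emergent bleeding AE, grouped by the MedDRA haemorrhage SMQ in the version used at database lock, with the term list fixed before unblinding.
- **Columns:** placebo, 2 g, 4 g and both doses pooled, each with the difference from placebo and its 95% CI. The single-dose columns serve the interest in dose-dependency stated in Protocol 1.2.
- **Periods:** the 12-week, 24-week and whole-treatment windows already defined for AEs.
- **Status:** labelled descriptive, with no multiplicity claim.

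The cost is one table from AE data that are coded anyway, with no new visits, samples or change to patient management. The downside is one more unadjusted comparison, which may show a chance difference in either direction.
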